### **5.6 Bias Control Measures**

**Multicenter:** Subjects from multiple institutions are more representative than that from single institution, which may avoid the bias of trial results due to systematic error of single institution.

**Randomization:** Randomization allows subjects to have equivalent opportunity to be assigned to the investigational group or the control group without the influence of the subjective will of the investigators and / or subjects. It can make the distribution of various influence factors similar and avoid selection bias and information bias as far as possible. In this trial, randomization method will be used to reduce the trial bias caused by the sampling error. Eligible subjects will be randomized to the investigational group or the control group to receive study treatment after the investigator has verified the inclusion and exclusion criteria. Random number table was generated by biostatistician using PLAN procedure of SAS before first subject enrollment. The detailed randomization method will be documented in the randomization specification.

**Parallel Control:** Parallel control design will be used in this trial. The investigational group and control group will be carried out at the same period to make factors that may influence the efficacy judgment distribute evenly between two groups.

**Training for the Investigator:** Before the clinical trial, Clinical Research Associates (CRAs) will coordinate with person in charge of each investigational institution to provide training about study protocol for the investigators to make the investigators understand and be familiar with the investigational medical device, to perform inclusion and exclusion criteria strictly, to complete appropriate examinations according to the requirements of the protocol and to master all new information related to this device found during the clinical trial, thus to reduce interference factors as far as possible.

Monitoring of the Trial: CRAs designated by sponsor create a monitor plan and perform on-site monitor visit regularly at the investigational institutions to make sure all contents in the study protocol are followed strictly, and check data in original source documents to make sure consistency with that in electronic case report form (eCRF).

Blinding of independent assessor: In this trial, independent assessors will be blinded to reduce measurement bias from outcome indicator measurers. The 3D images collected from each site will be aggregated into a single database without any randomization information. The aggregated images will be analyzed /measured by the independent assessor so as to achieve the blinding of independent assessors. Before the clinical trial, independent assessors shall complete the training on 3D wound imaging system. Independent assessors will not participate in randomization processing or patient treatment. The independent assessors will not be allowed to discuss the randomization results with any non-blinding study personnel and have no access to any study documents that may lead to unblinding.

## **6 Statistical Considerations**

### **6.1 Sample Size Calculation**

Up to 170 eligible subjects will be enrolled into the trial.

#### **6.1.1 Total Sample Size**

The number of evaluable subjects required for this trial is 128 subjects (64 per treatment arm). To account for a potential 10% drop-out rate, at least 140 subjects (70 per treatment arm) will be randomly assigned in a 1:1 allocation ratio to V.A.C. VERAFL™ or control group. 140 subjects (70 per study arm) will achieve approximately 80% power to detect a difference with a non-inferiority margin of 20% based on a one-sided t test with a significance level of 0.025 and pooled standard deviation being 40%.

Due to the uncertainty in the actual variability and trying to limit the study size to those strictly needed, a blinded sample size re-estimation will be performed after 50% evaluable subjects per arm (70 evaluable subjects total) have completed End of

Treatment Visit.

This number of subjects is expected to provide a sufficiently precise calculation of the variability in the actual study population. The point estimate for the pooled standard deviation will be used for the sample size re-estimation.

If the re-estimated sample size is greater than 140, the sample size may be increased up to a maximum of 200 subjects to provide sufficient power for this study. If the re-estimated sample size is less than 140, the sample size of the study is still 140.

To account for a higher than initially estimated drop-out rate of 25%, up to 170 subjects (85 per treatment arm) will be randomly assigned in a 1:1 allocation ratio to V.A.C. VERAFLTM or control group. 170 subjects (85 per study arm) will achieve 80% power to detect a difference with a non-inferiority margin of 20% based on a one-sided t test with a significance level of 0.025 and pooled standard deviation being 40%.

### **6.1.2 The Level of Significance and the Power of the Clinical Trial**

The level of significance is one-side 0.025. The power of the clinical trial is 0.8.

### **6.1.3 Expected Drop-out Rate**

Drop-out includes all conditions that cannot be included in the primary endpoint analysis finally, which refers to major protocol deviations judged by the investigator.

An expected rate of drop-out is about 25%.

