#### **5.1.2.4 Rationale of Blinding Selection**

This trial is set as open label, since the inconsistent packaging appearance of the devices between the two groups, the investigators and the subjects could not be blinded.

In this trial, independent assessors will be blinded to reduce measurement bias from outcome indicator measurers. 3D images collected from each site will be aggregated into a single database. The aggregated images will be analyzed / measured by the independent assessor so as to achieve the blinding of independent assessors.

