## 6.2 Analysis Data Set

**Full Analysis Set (FAS):** including all subjects randomized to receive either V.A.C. VERAFLTM Dressing Kit or control treatment. It is the secondary analysis set for efficacy evaluation, such as the time to completion of wound bed preparation, rate of wound area reduction, and changes in granulation tissue.

**Per Protocol Set (PPS):** PPS is the subset of the FAS. It is the primary analysis data set for efficacy evaluation.

**Safety Set (SS):** including all subjects who have received either V.A.C. VERAFLTM or control treatment. The data set is used to evaluate the safety of this trial.

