## 6.3 Subject Exclusion Criteria

PPS is a subset of FAS, including subjects who have received the treatment specified in the protocol, the observation data of the primary endpoint are available, and there are no significant protocol deviations affecting the primary efficacy endpoint. The rules for exclusion of subjects from PPS are as follows:

- (1) Missing baseline volume measure;
- (2) Missing end-of-treatment (EOT) volume measure;
- (3) Not completing the study (evaluable subjects will have completed the study if deemed ready for closure by investigator or had a treatment duration of up to 14 days);
- (4) Violating wound size inclusion criterion (maximum depth at baseline < 0.8cm or wound dimensions less than 8cm by 1cm) as determined by Independent Assessor (IA);
- (5) Baseline or EOT wound volume measures deemed unreliable after image review (i.e. laser line coverage inadequate, or depth unreliable, or poor margin visibility, or entire wound not imaged, or no comparison across time possible);
- (6) Major protocol deviations that would impact the primary endpoint as judged by the medical monitor. For example, the occurrence of post-baseline study wound debridement.

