6. ANALYSIS SETS

Agreement and authorization of subjects included/ excluded from each analysis set will be conducted prior to database lock. Prior to the blinded check of the sample size assumptions, the agreement and authorization of subjects excluded/included from the primary dataset (that is, identifying the evaluable subjects) will also be conducted.

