6.1. PER PROTOCOL SET (PPS)

PPS is the subset of the FAS, including subjects randomized to receive either VAC VERAFL0 or control treatment who do not have major protocol deviations impacting the primary efficacy analysis. It is the primary analysis set for efficacy evaluation.

The rules for exclusion of subjects from the per protocol set (PPS) are as follows:

- Missing baseline volume measure
- Missing end-of-treatment (EOT) volume measure
- Not completing the study (evaluable subjects will have completed the study if deemed ready for closure by investigator or had a treatment duration of up to 14 days*)
- Violating wound size inclusion criterion (maximum depth at baseline < 0.8cm or wound dimensions < 8cm by 1cm) as determined by Independent Assessor (IA)
- Baseline or EOT wound volume measures deemed unreliable after image review (i.e. laser line coverage inadequate, or depth unreliable, or poor margin visibility, or entire wound not imaged, or no comparison across time possible)
- major protocol deviations that would impact the primary endpoint as judged by the medical monitor. For example, post-baseline study wound debridement.

* actual treatment durations of evaluable subjects may be greater than 14 days. Minor protocol deviations should be written for treatment durations outside of the protocol defined window.

There are major PDs defined in the medical monitoring plan (MMD) that do not impact the primary efficacy endpoint. For example, major PDs related to informed consent do not impact the primary efficacy endpoint or interpretation of the primary efficacy analysis.

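### The protocol names two different people to judge exclusion from the primary analysis set, and neither document requires that judgement, or sign-off of the sets, to be blind to treatment arm

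*Protocol*

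**What the plan says.** **Who judges.** Protocol 6.1.3, in the sample-size section, counts as drop-out everything that keeps a subject out of the primary endpoint analysis, "which refers to major protocol deviations judged by the investigator". Protocol 6.3, rule 6, excludes from the PPS "Major protocol deviations that would impact the primary endpoint as judged by the medical monitor". SAP 6.1 repeats that rule: "major protocol deviations that would impact the primary endpoint as judged by the medical monitor". SAP 2 records no change from the protocol.

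**What the set is for.** Of the PPS, Protocol 6.2 says: "It is the primary analysis data set for efficacy evaluation". SAP 6.1 and 15.1.3 agree.

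**Who is masked.** Protocol 5.1.2.4 says that "the investigators and the subjects could not be blinded". The only masked role is the reader of the 3D images: under Protocol 5.6, "independent assessors will be blinded to reduce measurement bias from outcome indicator measurers".

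**When and by whom the sets are fixed.** SAP 6 says: "Agreement and authorization of subjects included/ excluded from each analysis set will be conducted prior to database lock". It also has evaluable subjects agreed before the blinded sample-size check. It does not say who agrees or what they may see. Protocol 8.3 describes a joint data review before lock by the data manager, principal investigators, statistical staff, sponsor and monitoring management. It then says that assignment to analysis sets follows the SAP definitions.

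**The concern.** Dropping subjects from the primary set after randomization is safe only if the decision cannot depend on the arm. Here one sentence gives that decision to people who know the arm and watch the wound, and the sections that name someone else do not say what that person may see.

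Rule 6 is the discretionary rule. Its own example is debridement of the study wound after baseline, and Protocol 5.2.3 links renewed debridement to a worsening wound. The rule therefore acts on subjects likely to have poor volume results. If it were applied more readily in the investigational arm, the remaining subjects would look better and the lower confidence limit would move away from -20 points, towards a finding of non-inferiority.

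**Working it through.** **1. The six PPS exclusion rules (Protocol 6.3; the same list is in SAP 6.1)**

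| Rule | Decided by | Room for arm-dependent judgement |
|---|---|---|
| 1. Baseline volume missing | Fact | Little |
| 2. End-of-treatment volume missing | Fact | Little |
| 3. Study not completed | Largely fact | Little |
| 4. Wound below the size criterion | Independent assessor, blinded | Little |
| 5. Volume unreliable on image review | Nobody named | Some, unless the blinded assessor decides |
| 6. Major deviation affecting the primary endpoint | Medical monitor (6.3, SAP 6.1); investigator (6.1.3) | Yes; no masking stated |

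The gap lies in rule 6, in rule 5 for want of a named decision-maker, and in the sign-off step.

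**2. The plan's own figures**

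Inputs from Protocol 6.1: margin 20 points, SD 40 points, one-sided alpha 0.025, power 0.80, 1:1 allocation, drop-out about 25%, at most 170 randomized.

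- Normal approximation: n per arm = 2 × (1.960 + 0.842)² × 40² / 20² = 62.8, so 63. The t-based calculation gives 64 per arm (power 0.801), which is the plan's 128.
- Inflation for 25% drop-out: 128 / 0.75 = 170.7, so 171, against 170 stated.
- Expected outside the PPS: 0.25 × 170 = 42.5, or about 42 subjects. This covers all six rules. No document says what share falls under rule 6.

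**3. What arm-dependent exclusion could do (assumed patterns)**

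The documents give no exclusion pattern, so a range is shown. Let f be the extra fraction of the investigational arm excluded, with nothing matching it in the control arm. Let D be how far those subjects average below their arm mean. The analysed number is held at 64 per arm, the SD at 40, and the true difference at -20. At f = 5%, about 64 × 0.05 / 0.95 = 3.4 extra subjects are excluded.

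- Shift in the arm mean = f / (1 - f) × D
- SE = 40 × √(2/64) = 7.07
- One-sided type I error = 1 - Φ(1.960 - shift / SE)

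For f = 5% and D = 40: shift = 0.05 / 0.95 × 40 = 2.11, and 1 - Φ(1.960 - 2.11 / 7.07) = 0.048.

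| f | D = 20: shift, error | D = 40: shift, error | D = 60: shift, error |
|---|---|---|---|
| 2% | 0.41, 0.029 | 0.82, 0.033 | 1.22, 0.037 |
| 5% | 1.05, 0.035 | 2.11, 0.048 | 3.16, 0.065 |
| 10% | 2.22, 0.050 | 4.44, 0.092 | 6.67, 0.155 |

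With no extra exclusion the error is 0.025. An identical pattern in the control arm would cancel the shift, so the table measures only the part of the exclusions that depends on arm.

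**The case against.** The strongest reply is that the conflict is one stray sentence. Protocol 6.1.3 plans a drop-out rate and is not an analysis-set rule. Both PPS definitions name the medical monitor, and Protocol 8.3 makes the SAP govern. This stands. A reader might infer that investigators choose the primary set; the documents do not support that. The sentences might also be read as two steps, with the investigator grading a deviation as major and the monitor judging its effect on the endpoint. But SAP 6.1 refers the definition of major deviations to the medical monitoring plan, not to the investigator, so 6.1.3 still needs correcting.

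Nor do the documents say that the medical monitor sees arm or volume results. The medical monitoring plan is not among the documents reviewed and may narrow the discretion or provide for masking. What can be said is that the protocol and SAP, which define the set, do not require masking.

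The existing checks are real. Agreement before lock prevents selection after the final comparison has been run. SAP 15.1.4 repeats the primary model on the full analysis set with multiple imputation, LOCF and NOCB, which brings rule-6 exclusions back in. SAP 9 tabulates set membership by arm, and SAP 10 lists deviations with PPS status, so an imbalance would be visible. It would therefore be wrong to call lock no safeguard. But in an open-label trial, timing alone hides neither the arm nor the wound's course, and the full-set analyses are only sensitivity analyses. No rule says what follows if they disagree with the PPS.

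**Conclusion.** The point holds in a limited form. The protocol contradicts itself on who judges, although the operative text is clear. The more important gap is that nothing requires rule-6 judgements or set sign-off to be blind to arm, in an open-label non-inferiority trial whose primary set is the PPS. The possible bias is reduced by existing safeguards but not removed.

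Its size cannot be derived from the documents. At an assumed extra 5% excluded from the investigational arm, 20 to 60 points below the arm mean, type I error at the margin would be about 0.035-0.065 instead of 0.025. That rests on a normal approximation, SD 40, 64 analysed per arm and no offsetting control exclusions. It illustrates sensitivity and does not predict what will happen.

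Two further inferences should be avoided. The roughly 42 subjects expected outside the PPS are not 42 discretionary exclusions. And masking would not make PPS membership independent of outcome: the debridement example in rule 6 is tied to wound worsening whoever decides. Masking removes only the discretion that depends on arm.

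**What to change.** - **Protocol 6.1.3:** name the medical monitor, to match Protocol 6.3 and SAP 6.1.
- **SAP 6:** state who signs off the PPS, and that sign-off uses listings masked to treatment arm, both before the blinded sample-size check and before database lock.
- **Rule 6:** state that these judgements are made masked to arm and also to the volume reduction results.
- **Rule 5:** state that the blinded independent assessor decides whether an image-based volume is reliable.

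Masking to volume should be confined to rule 6. Rules 1, 2 and 5 ask whether a volume exists and can be trusted, and the sample-size check needs the pooled SD of volume reduction in evaluable subjects.

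The cost is a few sentences and the work of preparing masked listings at two time points. Sample size, endpoint and clinical procedures do not change.

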### **6.1.4 Sample Size Allocation**

#### **6.1.4.1 Study Numbers for Each Type of Disease and Rationale**

Not applicable.

#### **6.1.4.2 Sample Size of Each Institution**

No one site can have more than 50% of total subjects enrolled (85 subjects).

### **6.1.5 Pass/Fail to be Applied to the Primary Endpoint**

When lower limit of the 95% confidence interval is greater than -0.20, it will be concluded that the V.A.C. VERAFLTM Dressing Kit is non-inferior to the control. The -0.20 margin was based on clinical judgement as the minimum difference in the primary endpoint values that can be considered meaningful.

## 6.2 Analysis Data Set

**Full Analysis Set (FAS):** including all subjects randomized to receive either V.A.C. VERAFLTM Dressing Kit or control treatment. It is the secondary analysis set for efficacy evaluation, such as the time to completion of wound bed preparation, rate of wound area reduction, and changes in granulation tissue.

**Per Protocol Set (PPS):** PPS is the subset of the FAS. It is the primary analysis data set for efficacy evaluation.

**Safety Set (SS):** including all subjects who have received either V.A.C. VERAFLTM or control treatment. The data set is used to evaluate the safety of this trial.

## 6.3 Subject Exclusion Criteria

PPS is a subset of FAS, including subjects who have received the treatment specified in the protocol, the observation data of the primary endpoint are available, and there are no significant protocol deviations affecting the primary efficacy endpoint. The rules for exclusion of subjects from PPS are as follows:

- (1) Missing baseline volume measure;
- (2) Missing end-of-treatment (EOT) volume measure;
- (3) Not completing the study (evaluable subjects will have completed the study if deemed ready for closure by investigator or had a treatment duration of up to 14 days);
- (4) Violating wound size inclusion criterion (maximum depth at baseline < 0.8cm or wound dimensions less than 8cm by 1cm) as determined by Independent Assessor (IA);
- (5) Baseline or EOT wound volume measures deemed unreliable after image review (i.e. laser line coverage inadequate, or depth unreliable, or poor margin visibility, or entire wound not imaged, or no comparison across time possible);
- (6) Major protocol deviations that would impact the primary endpoint as judged by the medical monitor. For example, the occurrence of post-baseline study wound debridement.

## **6.4 Criteria for the Termination of the Clinical Trial on Statistical Grounds**

The interim analysis is not planned for the trial, thus the trial will not be terminated due to statistical reasons.

## **6.5 Statistical Design, Method and Analytical Procedures**

The descriptive statistics of continuous variables include number, mean, standard deviation, median, minimum and maximum. Frequency and percentage will be used in the descriptive statistics for categorical variables. Unless otherwise specified, all statistical tests will be performed at a significance level of 2.5% (one-sided) with 95% confidence interval (CI).

Detailed statistical methods will be further demonstrated in the statistical analysis plan (SAP).

All statistical analyses will be performed using Statistical Analysis System (SAS) 9.2 version or a later version after database locked according to SAP.

### **6.5.1 Statistical Analysis Method**

#### **Primary efficacy endpoint**

The statistical hypothesis for testing the treatment group difference for primary efficacy endpoint is presented as follows:

- $H_0: M_T - M_C \leq -0.20$  tested against the alternative hypothesis
- $H_1: M_T - M_C > -0.20$

where:

$M_C$  is the means in control group and  $M_T$  is the means in to V.A.C. VERAFLTM group.

A two-sided 95% confidence interval for  $M_T - M_C$  will be constructed using the method of ANCOVA with treatment group, site, and treatment-by-site interaction (if the interaction effect is not statistically significant, then it will be removed from the final model) as fixed factors, and wound size ( $<15\text{cm}^2$ ,  $15\text{-}30\text{cm}^2$   $>30\text{cm}^2$ ) as covariate. If the lower limit of the 95% confidence interval is greater than -0.20, then it will be concluded that the V.A.C. VERAFLTM Dressing Kit is non-inferior to the approved control dressing in China (Local) + wall suction.

A rejection of the null hypothesis will trigger superiority testing based upon treatment difference. If the lower limit of the CI is greater than zero, V.A.C. VERAFL™ Dressing Kit is proven to be superior to China (Local) + wall suction.

The two hypothesis tests are hierarchically structured so that the second test (superiority) will only be considered if the first test (non-inferiority) is rejected. There is no alpha adjustment for the second test as a result of the hierarchical testing.

A primary analysis will be conducted on the PPS population, and sensitivity analysis will be conducted on the primary endpoints using the FAS population.

If the treatment-by-site interaction in ANCOVA model is significant, it always reveals that there is the heterogeneity of substantial treatment in different sites. In order to explain the heterogeneity influence for reliability of statistical conclusion, the descriptive statistics will be reported by different site.

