##### **4.1 Primary Objective**

The primary objective is to demonstrate non-inferiority in the wound volume reduction rate of investigational group versus control group patients with open wounds that have extensive soft tissue damage.

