### **5.2.3 Criteria and Procedures for Subject Withdrawal**

#### **1) Dropout Criteria**

Definition: A subject in the clinical trial who for any reasons fails to continue in the study until the last visit required of him/her by the study protocol.

If meet the following situations:

- Lost to follow-up.
- Subjects withdraw their informed consent and voluntarily withdraw from the trial:  
Subjects could withdraw from the trial voluntarily if they could not endure the AE, think the treatment is not effective, and want to take other treatments or without any reason.
- When the investigator judged that the risk is greater than the benefit if subject continues to participate in the trial, or the subject cannot continue the clinical trial

in the following conditions, for example a subject has abnormal organ dysfunction, allergic reaction, poor compliance, exacerbations, or a SAE needed to stop the trial treatment, and the subject should withdraw from the trial.

- The subject's target wound needs other treatment and should withdraw from the trial.
- If the target wound condition worsens (such as infection aggravated, anaerobic bacteria infection, etc.) in the use of investigational dressing or control dressing during the process of NPWT, after the investigator's evaluation of wound and treatment result, and if the surgical debridement is needed again, the NPWT will be stopped, the end of study assessments completed and the subject withdrawn from the study, then the target wound will be opened and debrided repeatedly, until the next intervention (such as delayed healing, surgical closure, graft et al) can be carried out.

Subjects have the right to withdraw from the trial at any time without any reason.

For all subjects terminate the trial in advance, the investigator should make every effort to obtain the reasons of withdrawal, e.g. AEs, unsuccessful correction therapy, withdrawing from the trial based on the investigator's judgment or other reasons, which should be recorded on the source documents. Subjects withdrawing from treatment in the trial should complete withdraw visit according to the schedule of visit procedure.

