15.1.3. PRIMARY ANALYSIS OF PRIMARY EFFICACY VARIABLES

PPS population is the primary efficacy analysis population. Descriptive statistics of actual wound volume, wound volume changes (wound volume before study treatment –wound volume of each visit) and wound volume reduction rate at visit (wound volume before initial study treatment –wound volume at visit)÷wound volume before initial study treatment×100% by visits, treatment group and overall will be provided.

Listings of actual wound volume will be presented and sorted by subject id, treatment group and visit.

The statistical hypothesis for testing the treatment group difference for primary efficacy endpoint is presented as follows:

- $H_0: M_T - M_C \leq -0.20$ tested against the alternative hypothesis
- $H_1: M_T - M_C > -0.20$

where:

M_C is the means in control group and M_T is the means in to V.A.C. VERAFLTM group.

A two-sided 95% confidence interval for $M_T - M_C$ will be constructed using the method of ANCOVA with treatment group, center, and treatment-by-center interaction (if the interaction effect is not statistically significant, then it will be removed from the final model) as fixed factors, and wound size (wounds surface area, <15cm² (ref) , 15-30cm², and >30cm²) as covariate.

The following statistics will be presented: LS Means, difference of the LS Means as well as its two-sided 95% CI, p-value for LS Mean difference. If the lower limit of the two-sided 95% confidence interval of difference is greater than -0.20, then it will be concluded that the V.A.C. VeraFloTM Dressing Kit is non-inferior to the approved control dressing in China (Local) + wall suction.

A rejection of the null hypothesis will trigger superiority testing based upon treatment difference. If the lower limit of the CI is greater than zero, V.A.C. VERAFLTM Dressing Kit is proven to be superior to control dressing.

The two hypothesis tests are hierarchically structured so that the second test (superiority) will only be considered if the first test (non-inferiority) is rejected. There is no alpha adjustment for the second test

as a result of the hierarchical testing.

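### Superiority would be concluded from the per-protocol interval, which leaves out subjects withdrawn for a worsening wound, while the planned FAS analyses enter no decision rule

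*Protocol*

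**What the plan says.** The stated aim is non-inferiority: "The primary objective is to demonstrate non-inferiority in the wound volume reduction rate of investigational group versus control group" (Protocol 4.1). Superiority enters only through the testing sequence.

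- **Testing rule.** SAP 15.1.3 says "A rejection of the null hypothesis will trigger superiority testing based upon treatment difference". The protocol's condition is "If the lower limit of the CI is greater than zero", read from the same ANCOVA interval and without alpha adjustment. Both documents then describe superiority as proven.
- **Analysis set.** SAP 15.1.3 opens with "PPS population is the primary efficacy analysis population", and Protocol 6.5.1 agrees: "A primary analysis will be conducted on the PPS population, and sensitivity analysis will be conducted on the primary endpoints using the FAS population". The superiority sentence names no set of its own, so it inherits the PPS.
- **Who leaves the PPS.** Protocol 6.3 lists "Not completing the study (evaluable subjects will have completed the study if deemed ready for closure by investigator" among the exclusions, and gives debridement of the study wound after baseline as its example of an excluding major deviation. SAP 6.1 has the same rules.
- **Withdrawal for worsening.** Under Protocol 5.2.3, if the wound worsens and debridement is needed again, "the NPWT will be stopped, the end of study assessments completed and the subject withdrawn from the study". The investigator makes that judgement, and Protocol 5.1.2.4 says "the investigators and the subjects could not be blinded".
- **FAS.** SAP 15.1.2 and 15.1.4 repeat the primary analysis in the FAS by multiple imputation (MI), LOCF and NOCB, as sensitivity analyses. Protocol 6.2 defines the FAS as all randomised subjects; SAP 6.2 defines it as all treated subjects.
- **Withdrawal image.** Protocol 5.5.2.5 collects a 3D image at withdrawal, before any further treatment. SAP 7.3 assigns early termination data to a visit only for by-visit summaries.

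**The concern.** A per-protocol primary set is a common choice for non-inferiority. Superiority is different: it should rest on the groups as randomised. Here the deciding set is selected after randomisation, and part of that selection is itself a treatment outcome, namely a wound that got worse.

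If more such failures occur in the investigational arm, the subjects who remain in the PPS look better than the arm as a whole did. Superiority could then be reported as proven, in a registration trial, when all randomised subjects show no difference. Nothing in the pass/fail rule (Protocol 6.1.5) or in SAP 15.1.4 says what to conclude if the FAS result points the other way.

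**Working it through.** **1. The plan's own figure.** Inputs from Protocol 6.1.1 and 6.1.2: margin 20 points, SD 40, one-sided 0.025, 64 evaluable per arm.

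- SE = 40 × √(2/64) = 7.07 points.
- Noncentral t, df 126, noncentrality 20/7.07 = 2.83: power 0.801. With 63 per arm it is 0.795. So 128 evaluable subjects is reproduced.
- The 95% half-width at 64 per arm is 13.99 points. Superiority is therefore declared at an observed PPS difference just above 14 points.

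**2. False superiority in the PPS.** The documents give no failure rates by arm and no outcomes for failures, so these inputs are assumptions: control completers average a 50% reduction, failures average f = 0% or 25%, and 64 per arm remain in the PPS. Let pC and pT be the failure rates. No difference in all randomised subjects requires

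μT = [50(1 − pC) + f·pC − f·pT] / (1 − pT), and the PPS difference is μT − 50.

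Example: pC = 0, pT = 10%, f = 0 gives μT = 50/0.90 = 55.56, a PPS difference of 5.56 and a noncentrality of 5.56/7.07 = 0.79. Superiority is declared in 11.9% of trials.

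| Failure pattern | PPS difference (f = 25; f = 0) | Superiority declared |
|---|---|---|
| Equal in both arms | 0; 0 | 2.5% |
| Investigational +2 points (pC = 0) | 0.51; 1.02 | 3.0-3.5% |
| Investigational +5 points (pC = 0) | 1.32; 2.63 | 3.8-5.6% |
| Investigational +10 points (pC = 0) | 2.78; 5.56 | 5.8-11.9% |
| Control +5 points (pT = 0) | -1.25; -2.50 | 1.0-1.6% |
| Control +10 points (pT = 0) | -2.50; -5.00 | 0.4-1.0% |

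If control failures are 5% instead of none, the 5- and 10-point investigational excesses give 3.9-5.8% and 6.1-12.8%.

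**3. The FAS under the same assumptions.** Simulation with 85 randomised per arm, all outcomes observed and an unadjusted t interval gives false superiority of 2.4-2.6%.

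**4. Can the two sets disagree?** Suppose the PPS lower limit sits at 0 (difference 14.0), with 30% of the investigational arm and 20% of the control arm excluded, and excluded subjects averaging 40 points less reduction than retained ones. The all-randomised difference is 14.0 − (0.30 − 0.20) × 40 = 10.0. With 85 per arm the half-width is 12.1, so the FAS lower limit is 10.0 − 12.1 = -2.1. The plan has no rule for this case.

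**5. Would the planned FAS analyses use the failure's outcome?** For a subject imaged at withdrawal, LOCF would normally carry that image forward. For MI the plan does not say whether the image is the outcome or is replaced by an imputed value. MI that treats failures like completers would not remove the bias.

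**The case against.** The strongest reply is that the FAS analyses already exist. SAP 15.1.4 applies the same method, including the superiority step, in the FAS by three approaches, so a conflict would be visible in the report. That is right, and a reader who inferred that the plan ignores excluded subjects would be wrong. What is missing is decision status: the conclusion follows from the PPS whatever the FAS shows.

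Three further replies stand and limit the point.

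- The inflation is conditional. No document suggests more failures in the investigational arm. The planned 25% loss cannot be read as a failure rate either, because it also covers losses such as missing or unreliable images and wound-size violations.
- Not every exclusion is decided by someone who knows the arm. Under Protocol 6.3 the medical monitor judges deviations and the independent assessor, who reads images blinded, judges wound size. SAP section 6 settles the sets before database lock. The concern about unblinded decisions applies to withdrawal.
- Superiority is not an objective, and the trial is sized for non-inferiority.

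A reader might also infer that the PPS is the wrong primary set for non-inferiority. Nothing here supports that.

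**Conclusion.** The point holds for superiority only. The rule as written can declare superiority from a set that removes treatment failures, and a contrary FAS result has no stated consequence. With an investigational-arm failure excess of 2, 5 or 10 points, the nominal 2.5% becomes 3.0-3.5%, 3.8-5.6% or 5.8-11.9%. It stays at 2.5% with equal failure and falls below that with a control-arm excess. All these figures rest on the assumed completer and failure means and on 64 per arm with SD 40. It would be too strong to say that the planned test is known to be inflated, because the documents do not give the direction or the size of any imbalance. The non-inferiority conclusion is not affected. The change is worth making before database lock, because it costs little and the superiority claim would otherwise be unqualified.

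**What to change.** Change SAP 15.1.3 and record the change in SAP section 2, as Protocol 6.6 allows before lock. Align the output templates too, because SAP section 8 gives them priority over the SAP text. Change Protocol 6.5.1 as well if the protocol is amended. Suggested content:

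1. Superiority is tested only after non-inferiority is shown in the PPS. It is concluded only if the lower limit of the two-sided 95% interval exceeds 0 in the FAS, analysed as randomised. The PPS superiority result is supportive.
2. For any subject who withdraws or stops study treatment early, for whatever reason, a usable 3D volume from the withdrawal visit is the outcome in this FAS analysis. MI is used only where no usable image exists. State openly that this takes the volume at treatment stop as the outcome.
3. If superiority in the PPS is not matched in the FAS, report that superiority was not shown.
4. Use the Protocol 6.2 definition of the FAS (all randomised) in SAP 6.2.

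Requiring both sets to exceed 0 is not needed. The FAS alone holds about 2.5%, while the double requirement gives about 1.3% with equal failure and costs power.

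**Cost.** SAP and template wording, plus an ethics-approved amendment if the protocol text is edited. No new visits or data. Non-inferiority power is unchanged. Superiority power depends on failures. The table assumes a 20-point advantage in completers, equal failure rates, failures at 0%, 85 randomised per arm and all FAS outcomes observed.

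| Failures in each arm | FAS | Both sets | PPS |
|---|---|---|---|
| 0% | 90% | 79% | 80% |
| 2% | 87% | 77% | 80% |
| 5% | 83% | 75% | 80% |
| 12.5% | 72% | 67% | 80% |
| 25% | 53% | 51% | 80% |

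FAS power is lower than shown if losses have no usable image.
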